8.4 Medical history

For phase I and phase II, medical history will be coded according to MedDRA (version 23.0 or higher).

The number and percentage of subjects experiencing a medical history will be summarized by the MedDRA System Organ Class and Preferred Term. Subjects reporting more than one condition/diagnosis within a System Organ Class will be counted only once for that System Organ Class.

For phase I, medical history will be based on the safety analysis set; and for phase II, medical history summaries will be based on the full analysis set.

8.5 Prior and Concomitant Medications/Procedures

For phase I, medication/procedure summaries will be based on the safety analysis set; and for phase II, medication/procedure summaries will be based on the full analysis set. All medications will be coded using WHOdrug global B3, 201903 or higher.

Medications used in the study will be classified in two parts:

1. Prior medication: medication that ended before the first dose of study drug, regardless of when dosing of the medication started.

2. Concomitant medication: medications ended after or on the first dose of study drug or medication with missing stop date, regardless of when dosing of the medication started.

The following medication categories will also be summarized by ATC2 and preferred term.

1. Prior Anti-tumor Medication
2. Prior Non-Anti-tumor Medication
3. Post-Treatment Anti-tumor Medication

Missing or partial dates will be imputed for medication. Algorithm for missing or partial start date is:

Missing day: first day of the month is imputed;

Missing month: January is imputed;

Missing year: not imputed.

Algorithm for missing or partial end date is:

Missing day: last day of the month is imputed;

Missing month: December is imputed (31 December if day is also missing);

Missing year: not imputed.

Missing data algorithms will be reviewed to ensure the algorithm works. For example, end date will not be before the start date after the imputation.

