6.4.3 Prohibited concomitant therapy

Anticancer therapy (chemotherapy, biologic or radiation therapy, surgery or Chinese medicine/Chinese patent medicine with anti-tumor effect) other than the study treatments must not be given to patients while the patient is on the study. If such agents are required for a patient, then the patient must be discontinued from the study.

In vitro data indicate Drug HH2710 is metabolized primarily by CYP3A, therefore strong inhibitors of CYP3A4 (e.g., clarithromycin, itraconazole, ketoconazole, telithromycin, etc.) and strong CYP3A4 inducers (e.g., carbamazepine, rifampicin, St. John's wort, etc.) should be avoided. Gastric acid reducing agents and sensitive substrates of CYP2C8, CYP2C9, and CYP2C19 also should be avoided. Refer to [**Appendix 14.7**](#) for a list of prohibited medications. This list may not be comprehensive.

Current treatment with agents including vitamins, supplements, and herbal supplements that are metabolized solely through CYP3A4 should be prohibited.

In vitro data indicate HH2710 is a potential P-gp substrate. Strong P-gp inhibitor will likely increase the exposure level of HH2710. Strong P-gp inhibitor should be avoided (Refer to [**Appendix 14.8**](#)).

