7.1.5.2 Follow-up of survival

Telephone follow-up will be conducted every 3 months since the occurrence of progressive disease or the starting of new antitumor treatment to collect patients' information on subsequent antitumor treatment and survival condition. It was completed 1 year after disease progression or initiation of new anti-tumor therapy. If patients have started new antitumor treatment after the final dose prior to end-of-treatment visit, they will directly enter the survival visit without receiving the end-of-treatment visit.

If patients terminate treatment prior to the occurrence of progressive disease, they should take part in survival follow-up to collect patients' information on subsequent antitumor treatment and survival condition.

Patients lost to follow up should be recorded as such on the CRF. For patients who are lost to follow-up, the investigator should show "due diligence" by documenting in the source documents steps taken to contact the patient, e.g., dates of telephone calls, registered letters, etc.

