8.7.1.1 Best Overall Response

Best Overall Response (BOR) is defined as the best overall response recorded from the start of treatment until disease progression or initiation of alternative therapy or end of study. A summary of subjects achieving a best overall response in a given category (CR, PR, SD, PD, NE, and Missing) will be provided.

In phase II, BOR will be summarized by investigator.

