10.1 Appendix A Censor rule for PFS, DoR

No.	Situation	Events or Censor	Analysis date*
1	No baseline assessment	Censor	First dose date
2	No post-baseline assessment, no Death	Censor	First dose date
3	PD during the study (except #5, #7)	Events (PD)	PD date
4	Any kind of Death (except #5, #7)	Events (Death)	Death date
5	PD or Death after missed two consecutive assessment	Censor	Last assessment date before the missed two consecutive assessment
6	Have at least one post-baseline assessment, no PD, no Death	Censor	Last assessment date
7	Initiating alternative anti-cancer therapy	Censor	Last assessment date before initiating alternative anti-cancer therapy

* If there are multiple assessment date on one tumor assessment, choose the earliest assessment date when overall response is PD, and choose the latest assessment date when overall response is CR/PR/SD.

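### SAP 8.5 can impute a start of new anti-tumour therapy that falls before the progression scan; if the censoring rules use that date, a true progression becomes an earlier censoring

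*SAP*

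**What the plan says.** SAP 8.5 opens its date rule with "Missing or partial dates will be imputed for medication". For start dates the rule is "Missing day: first day of the month is imputed" and "Missing month: January is imputed". One of the medication categories just above it is "Post-Treatment Anti-tumor Medication", and no separate rule is given for that category. The section promises a review that the algorithms work; its one example is that an end date must not precede a start date.

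The start of new therapy matters in three places:

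- **Appendix A (PFS, DoR) and Appendix C (TTP).** Row 3 makes PD an event except where row 5 or row 7 applies. Row 7 censors a patient who starts other anti-cancer therapy at: "Last assessment date before initiating alternative anti-cancer therapy".
- **Appendix B (TTR).** Row 4 uses the same start date.
- **SAP 8.7.1.1.** Best overall response is counted "until disease progression or initiation of alternative therapy or end of study".

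SAP 8.1 adds that, unless otherwise specified, efficacy and safety data are not imputed, and that partial dates needed for computation are filled conservatively. Protocol 10.6.7.1 also asks for the most conservative value and gives the first of the month as its example for a start date. Appendix E defines PFS as running to progression or death whether or not the patient receives another anticancer therapy first.

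**The concern.** The first of the month is the earliest date compatible with the record. That is a common choice for adverse events, where it errs towards counting an event as treatment-emergent. For the start of new therapy it works the other way. New therapy usually follows progression, often within weeks, so moving the start back can place it before the scan that prompted it. Read in time order, row 7 then overrides row 3, and the patient is censored at the previous scan.

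Such censoring is informative, because it falls on patients who have just progressed, and it lengthens the estimated times.

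Partial dates are foreseeable. Under Protocol 7.1.5.2, "Telephone follow-up will be conducted every 3 months since the occurrence of progressive disease" (or since the start of new treatment), and these calls collect subsequent therapy. Protocol 6.4.3 says anticancer therapy "other than the study treatments must not be given to patients while the patient is on the study", so a start date before the last dose would usually point to a poor imputation. The adverse-event rule in SAP 8.8.1.1 has a floor at first dose; the medication rule has none.

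**Working it through.** The documents give no figure for this effect, so there is nothing to reproduce. The check counts how often the 8.5 date falls before the PD scan, **if** that date is used in row 7.

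**Inputs.** The imputation rule is from SAP 8.5, and the event and censoring rows are from Appendices A and C, read in time order. Scans are every 2 cycles of 21 days, so 42 days apart (Protocol 7.2.5). Assumptions: PD is equally likely on each day of a 365-day year, and new therapy starts a fixed gap of g days after PD.

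**Only the day missing.** In a month of L days, with PD on day d, the imputed start falls strictly before PD when d ≥ 2 and d + g ≤ L. That is max(0, L − g − 1) days per month. Summed over the year:

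| Gap g (days) | PD days affected | Share of 365 |
|---|---|---|
| 7 | 365 − 12 × 8 = 269 | 74% |
| 14 | 365 − 12 × 15 = 185 | 51% |
| 21 | 365 − 12 × 22 = 101 | 28% |
| 28 | 7 × 2 + 4 × 1 + 0 = 18 | 5% |
| 30 or more | 0 | 0% |

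Counting imputed dates that coincide with the PD scan would add about 12/365, or 3 points, at gaps of 7 to 21 days. The imputed date lies less than 42 days before PD, so the last earlier scan is always the previous one: each affected event is censored 42 days earlier.

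**Month also missing.** The imputed start is 1 January, and the share is (365 − g − 1)/365: 363/365 = 99.5% for a 1-day gap, 350/365 = 95.9% for 14 days and 322/365 = 88.2% for 42 days. Censoring moves about 184 to 204 days earlier on average if earlier scans exist.

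**Example.** First dose 1 March 2022, scans 12 April, 24 May and 5 July, PD on 5 July (day 127), new therapy 19 July.

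- Full date: event on day 127.
- Day missing: start set to 1 July, censored on 24 May (day 85).
- Month missing: start set to 1 January, before any on-treatment scan. Row 7 has no on-treatment date to use, and falling back to first dose gives day 1.
- If therapy instead began on 9 August with the day missing, the start is 1 August and the event is kept.

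**From records to events.** The share of PD events lost, among patients who start new therapy, is the share above times the share of start dates that are partial. The documents do not give the latter. Purely for illustration, with 5% to 30% partial and a 14-day gap: 0.507 × 0.05 = 2.5% to 0.507 × 0.30 = 15%.

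**The case against.** The strongest reply is that 8.5 serves the medication summaries and nothing links its dates to Appendices A-C. SAP 8.1 rules out imputation for efficacy unless specified and asks for a conservative choice where a date must be filled. This stands as far as it goes: a reader might infer that the SAP directs the 8.5 date into the censoring rules, and it does not say so. But 8.5 is the only medication-date rule in the SAP, and the protocol's example is also the first of the month, so a programmer would naturally use it. If 8.5 does not apply, row 7 has no working rule for a partial date. Either way the same text is needed.

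Other limits also stand:

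- A reader might infer that the imputed date generally precedes PD. It does so only when therapy starts in the same recorded month or year.
- A reader might call a start before the last dose impossible. It is only contrary to protocol: Protocol 7.1.4.1 lists concurrent antineoplastic therapy as a reason to stop treatment.
- A reader might conclude that censoring is the only use of a medication start date. The end-before-start check uses it, and deriving post-treatment status may as well.
- Under the Appendix E definition no PFS event would be lost, and DoR concerns responders only.
- A shortened response window could drop a confirmation scan, but that would lower ORR. The interim boundaries do not use medication dates directly.
- SAP section 7 records that the programme was stopped and many analyses may not be run. SAP 8.7.1.3 makes Kaplan-Meier analyses conditional on numbers. In Phase I, PFS and DoR are exploratory and TTP is not an endpoint.

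The planned review of the algorithms is a safeguard, but it names no check against PD or last dose. The listing of time-to-event endpoints is still promised in 8.7.1.3 and would carry the wrong status and date.

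**Conclusion.** The point holds in conditional form. The start-date rule in 8.5 suits summaries but, applied to row 7 of Appendices A and C, gives wrong results for patients whose new therapy began in the same recorded month (or year) as their PD. The size per partial record depends mainly on the gap: large within two weeks, negligible by four weeks when only the day is missing, and large at every gap examined when the month is missing. TTP and DoR are biased upward; PFS is too if Appendix A row 7 prevails over Appendix E. The overall effect cannot be stated, because neither the share of partial dates nor the distribution of gaps is in the documents, and early termination limits it further. The correction is still worth making: it is cheap, and with few patients each misclassified event weighs more.

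**What to change.** In SAP 8.5, cross-referenced in Appendices A-C, add for post-treatment anti-tumour therapy:

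1. A partial start date is imputed within the recorded month or year, as the later of the first day of that period and the day after the last HH2710 dose, when that day lies in the same period. The date is never moved outside the recorded period, so a recorded deviation is not hidden.
2. The imputed date may not precede a PD documented in the same known period, and on a tie PD stays the event.
3. One sensitivity analysis uses the last day of the known period.

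The second condition does the work: it brings the loss of PD events that truly preceded therapy to zero. The last-dose floor alone is not enough, because a patient may stop HH2710 without progression and show PD on a later follow-up scan.

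Also reconcile Appendix A row 7 with the Appendix E definition of PFS.

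The cost is a few sentences, one programming condition and one extra run. The downside is that if therapy truly began before PD within that period, the PD is counted as an event, which is the conservative direction.

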8.6 Study Drug Exposure

Total number of cycles is defined as the maximum number of treatment cycles that a subject receives. Total cumulative dose (mg) is the sum of the actual doses that the subject receives across cycles. Total planned dose (mg) is the sum of the planned doses.

Actual exposed weeks = (Last dosing day – first dosing day +1)/7;

Total planned Dose (mg) = Planned dose* (Last dosing day – first dosing day +1);

Planned exposed weeks = 21*number of cycles/7;

Relative dose intensity is defined as follows:

Relative dose intensity = (total cumulative dose/actual exposed weeks)/ (Total planned /planned exposed weeks) *100%

The total number of cycles, total cumulative dose (mg), total planned dose (mg), relative dose intensity and categorized as < 80%, 80% - 120%, >120% will be summarized for each component of the dosing regimen for phase I and phase II.

A dose reduction, dose interruption, dose withdrawn and their reasons will be summarized by treatment group for phase I and phase II.

The study drug exposure will be summarized based on the safety analysis set.

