6.1 Study treatment

A treatment cycle is defined as 21 days for the purposes of scheduling procedures and evaluations.

The investigational product in the study is shown as below:

- Active ingredient: HH2710;
- Strength: 25 mg capsule, 100 mg capsule;
- Excipients: include but not limit to Lactose, Silicified Microcrystalline Cellulose, Talc, Colloidal silicon Dioxide, Crospovidone, and Magnesium Stearate;
- Storage temperature: 10-30°C , protected from light.

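### SAP 8.6 spreads planned dose for actual dosing days over whole-cycle weeks, so relative dose intensity is wrong (too high if a started cycle counts) for a patient who stops mid-cycle

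*SAP*

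**What the plan says.** SAP section 8.6 (Study Drug Exposure) builds relative dose intensity (RDI) from these definitions:

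- Time on drug: "Actual exposed weeks = (Last dosing day – first dosing day +1)/7".
- Planned dose, in words: "Total planned dose (mg) is the sum of the planned doses". Planned dose, as a formula: "Total planned Dose (mg) = Planned dose* (Last dosing day – first dosing day +1").
- Planned time: "Planned exposed weeks = 21*number of cycles/7".
- Cycles: "Total number of cycles is defined as the maximum number of treatment cycles that a subject receives".
- The ratio: "Relative dose intensity = (total cumulative dose/actual exposed weeks)/ (Total planned /planned exposed weeks) *100" per cent.

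RDI is then tabulated in three classes: below 80%, 80% to 120%, and above 120%. Protocol section 6.1 supplies the cycle length: "A treatment cycle is defined as 21 days for the purposes of scheduling procedures and evaluations". SAP section 8.12 lists no change to RDI, and the protocol gives no definition of its own.

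**The concern.** RDI should compare the dose rate a patient received with the rate planned. Here the received rate is consistent: dose taken over the actual span, divided by the length of that span. The planned rate is not. Its numerator covers the actual span and its denominator covers whole cycles. For a patient who stops partway through a cycle, the planned rate is diluted by days on which no dose was planned in the numerator, so the ratio rises.

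Mid-cycle stops are to be expected. Dosing is continuous and runs until toxicity, progression, investigator decision or refusal (Protocol section 7.1.3), not for a fixed number of cycles. What is at stake is the RDI classification. Fully dosed patients could appear over-dosed, and under-dosed patients who stop early could appear adequately dosed. The table is shown by dose level in Phase I, where the escalation groups listed in Protocol section 1.2.1.2 had 3 or 4 patients. One misplaced patient in such a group moves a class by 25 to 33 percentage points (1/4 to 1/3).

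**Working it through.** The plan states no RDI value, so there is no figure to reproduce. The check substitutes the SAP's definitions into its own ratio.

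**Inputs (SAP 8.6 unless stated)**

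- A = total cumulative dose (mg)
- D = planned daily dose (mg)
- T = last minus first dosing day, plus 1
- C = number of cycles, each of 21 days (Protocol 6.1)
- Actual weeks = T/7; planned dose = D × T; planned weeks = 21C/7

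**Algebra**

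RDI = [A/(T/7)] ÷ [D × T/(21C/7)] = [A/(D × T)] × (21C/T)

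The first factor is the true dose ratio. The second equals 1 only when T = 21C. This result does not depend on how C is counted.

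**Assumption for the figures.** The SAP does not say whether an incomplete cycle counts. Taking a started cycle as received, C is T/21 rounded up.

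**Worked case: 300 mg QD, every dose taken, last dose on day 10**

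- Actual rate: 3000 mg ÷ (10/7 weeks) = 2100 mg/week
- Planned rate as written: 3000 mg ÷ 3 weeks = 1000 mg/week
- RDI = 2100/1000 = 210%; true ratio 3000/3000 = 100%

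**Other stopping days**

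| Share of planned drug taken | Last-dose day T | C | RDI as written | True ratio |
|---|---|---|---|---|
| 100% | 21 | 1 | 21/21 = 100% | 100% |
| 100% | 31 | 2 | 42/31 = 135% | 100% |
| 100% | 50 | 3 | 63/50 = 126% | 100% |
| 100% | 106 | 6 | 126/106 = 118.9% | 100% |
| 60% | 10 | 1 | 0.6 × 21/10 = 126% | 60% |
| 60% | 15 | 1 | 0.6 × 21/15 = 84% | 60% |
| 60% | 31 | 2 | 0.6 × 42/31 = 81.3% | 60% |

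**Days on which the class is wrong**

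- Full dosing exceeds 120% when 21C/T > 1.20, that is T < 17.5C. This gives days 1-17 (C = 1), 22-34 (C = 2), 43-52 (C = 3), 64-69 (C = 4) and 85-87 (C = 5). For C = 6 it would need T < 105, but the sixth cycle starts on day 106, so none from there on.
- 60% dosing exceeds 120% when T < 10.5C: days 1-10 only.
- 60% dosing reaches at least 80% when T ≤ 15.75C. After removing days 1-10, this leaves days 11-15, 22-31 and 43-47 in the middle class. On all other days the patient is correctly below 80%.

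These are possible last-dose days, not proportions of patients.

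**If only completed cycles count.** Full dosing to day 31 has C = 1 and RDI = 21/31 = 67.7%. A stop within cycle 1 has C = 0, so planned weeks are zero and RDI is undefined.

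**If the span outruns the cycles.** Suppose cycles are pushed back by a hold (the documents do not say), and two cycles of doses (42 dosing days) are taken over 52 days. The true ratio is 42/52 = 80.8%. RDI as written is (42/52) × (42/52) = 65.2%.

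**The case against.** The arithmetic is hard to contest; the stronger case concerns direction, reading and weight.

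- **Direction.** Inflation depends on counting a started cycle, which the SAP does not state. With completed cycles only, or with cycles delayed by a hold, the error runs the other way. This stands as a condition on the figures. It does not rescue the formula, which is then too low or undefined.
- **Reading.** The verbal definition of planned dose could mean a sum over whole planned cycles. That would give D × 21C, and the ratio would be correct. This also stands, but the explicit formula in the same section uses the actual span, and that is what a programmer would implement. Strictly, the fault is that two lines cover different periods; either could be changed.
- **Mitigation.** Cumulative dose and planned dose as printed (D × T) are both derived and summarised. Their quotient for each patient is the undistorted ratio, so the inputs for a correct figure already exist. Reductions, interruptions and withdrawals are also reported separately.
- **Values above 120%.** These are not always errors: Protocol section 6.2.3.3 allows intra-patient escalation after four cycles, which can raise RDI legitimately if planned dose means the assigned dose.
- **Weight.** SAP section 7 says that the programme has stopped and that many planned analyses may not be run.

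These points limit the importance of the error but do not remove it.

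**Conclusion.** The formula in SAP 8.6 is wrong as written. It multiplies the true dose ratio by 21C/T, and that is exact algebra. The upward direction and the day ranges assume that a started cycle counts as received, which is the natural reading but is not stated. On that reading the overstatement is largest for early stops (a factor of 2.1 at day 10) and too small to move a fully dosed patient out of the middle class from cycle 6 onwards.

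How many patients would be misclassified cannot be said, because the documents give no distribution of stopping days. The consequence is confined to the RDI row and its classes in a descriptive table. No endpoint, rule for choosing the Phase II dose, or sample size depends on it. Severity is minor.

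**What to change.** Make planned dose and planned time cover the same period. Either change works:

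1. Define RDI as total cumulative dose divided by total planned dose, times 100%, with both taken from first to last dosing day. The week terms are dropped.
2. Keep the ratio and change only the planned-dose line to planned daily dose × 21 × number of cycles. The planned rate becomes D × 21C ÷ (21C/7) = 7D, and RDI = [A/(T/7)]/(7D) = A/(D × T).

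Both give 100% for full dosing at T = 10, 31 and 50. C cancels in both, so RDI no longer needs a rule for partial cycles. The first is simpler and keeps the reported planned dose on the dosing interval. The second makes the reported planned dose cover whole cycles: for 300 mg QD stopped on day 10, 300 × 21 = 6300 mg planned against 3000 mg taken, although RDI itself is 100%.

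The SAP should also say that planned dose means the total daily dose, so that BID cohorts are handled correctly, and whether it is the assigned dose or the dose in force after a change.

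The cost is one line in the SAP and one in the program. As in the current formula, a hold after the last dose is not reflected, so RDI should still be read beside the interruption and withdrawal summaries.
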